5.1. Summary of Study Design

Study I1F-MC-RHCF (RHCF) is a Phase 3b/4, multicenter, randomized, open-label, parallel-group study with blinded outcomes assessments evaluating the efficacy and safety of ixekizumab versus adalimumab in patients with active psoriatic arthritis (PsA) who are naive of biologic disease-modifying anti-rheumatic drug (bDMARD) during a 52-week treatment period.

[figure not shown]
The study will consist of 3 periods:

- Period 1: Screening Period (Visit 1) up to 28 days before randomization (Visit 2)
- Period 2: Open-Label Treatment Period (Visit 2 through Visit 11) from Week 0 to Week 52
- Period 3: Post-Treatment Follow-Up Period occurring from the last treatment visit during Period 2 or Early Termination Visit (ETV) up to a minimum of 12 weeks after that visit

All patients randomized to ixekizumab will receive a starting dose of 160 mg at randomization (Visit 2 [Week 0]). Patients with moderate-to-severe plaque psoriasis will receive ixekizumab 80 mg every 2 weeks (Q2W) from Week 2 to Week 12 and every 4 weeks (Q4W) thereafter. Patients not meeting criteria for moderate-to-severe plaque psoriasis at randomization will receive ixekizumab 80 mg Q4W starting at Week 4.

Patients randomized to adalimumab with moderate-to-severe plaque psoriasis will receive a starting dose of 80 mg at randomization (Visit 2 [Week 0]) followed by 40 mg Q2W starting at Week 1. Patients not meeting criteria for moderate-to-severe plaque psoriasis will receive a starting dose of 40 mg at randomization (Visit 2) followed by 40 mg Q2W starting at Week 2 (see Section 7.1 of study protocol for details regarding treatments administered).

[Figure RHCF.5.1](#) illustrates the study design.

Abbreviations: D = days; LTV = last treatment visit during Period 2 or Early Termination Visit; n = number of subjects; V = visit; W = week.

^a See Section 7.1 of RHCF Study Protocol for dosing details.

Figure RHCF.5.1. Illustration of study design for Clinical Protocol I1F-MC-RHCF.

5.2. Determination of Sample Size

Approximately 550 patients who meet all criteria for enrollment at Visits 1 and 2 will be randomized in a 1:1 ratio at Week 0 (Visit 2) in Period 2 to ixekizumab or adalimumab (275 patients per treatment group).

Sample size was calculated assuming the proportion of patients simultaneously achieving 50% improvement in American College of Rheumatology criteria (ACR50) and 100% improvement from baseline in Psoriasis Area and Severity Index criteria (PASI 100) as 13.6% and 31.3% in the adalimumab and ixekizumab treatment groups, respectively, as observed in the conventional synthetic disease-modifying anti-rheumatic drugs (csDMARD)-experienced population from Study I1F-MC-RHAP (RHAP). According to the nQuery software, a total sample size of 550 (ie, 275 per treatment group) using a 2-sided Fisher's exact test at 0.05 level of significance would yield approximately 99% power for testing ixekizumab versus adalimumab.

This sample size would yield 78% power for testing the noninferiority of ixekizumab to adalimumab at a 1-sided 0.025 level of significance based on a noninferiority margin of -12% and using ACR50 response rates of 43.8% and 44.1% as observed for the ixekizumab and adalimumab treatment groups, respectively, in the csDMARD-experienced population from Study RHAP. For testing superiority of ixekizumab to adalimumab based on PASI 100 response rates of 46.9% and 23.7% as observed for ixekizumab and adalimumab in the csDMARD-experienced population from Study RHAP, this sample size would yield approximately 99% power using a 2-sided Fisher's exact test at 0.05 level of significance.

5.3. Method of Assignment to Treatment

Patients who meet all Visit 1 and Visit 2 eligibility criteria for enrollment will be randomized at Visit 2 (Week 0) in a 1:1 ratio to open-label treatment with ixekizumab or adalimumab at Week 0 (Visit 2). Assignment to treatment groups will be determined by a computer-generated random sequence using an interactive web-response system (IWRS). The IWRS will be used to assign investigational product to each patient. Site personnel will confirm that they have located the correct investigational product by entering a confirmation number found on the investigational product into the IWRS. The randomization will be stratified by concomitant csDMARD use at baseline (Yes, No) and moderate-to-severe plaque psoriasis involvement (Yes, No).

6. A Priori Statistical Methods

6.1. General Considerations

This plan describes a priori statistical analyses that will be performed. Statistical analysis of this study will be the responsibility of Eli Lilly and Company (hereafter Lilly). The statistical analyses will be performed using SAS® Version 9.2 or higher. Lilly will be responsible for producing the tables, figures, and listings, unless otherwise specified. All tables, figures, and listings will be checked independently for consistency and integrity by Lilly. This analysis plan also includes exploratory analyses that are intended to be produced separately from the clinical study report (CSR) outputs, as noted below.

Additional efficacy, health outcomes, and safety analyses for Health Technology Assessment (HTA) purposes will be described in a separate document, and results will be reported separately from the CSR.

Continuous data will be summarized in terms of the number of observations, mean, standard deviation (SD) and/or standard error of the mean (SEM), if applicable, median, minimum, and maximum. The minimum and maximum will be reported to the same number of decimal places as the raw data recorded in the database. The mean and median will be reported to 1 more decimal place than the raw data recorded in the database. The SD and SEM will be reported to 2 more decimal places than the raw data. In general, the maximum number of decimal places reported shall be 4 for any summary statistic.

Categorical data will be summarized in terms of the number of patients in the analysis population, the number of patients with non-missing data at the relevant time point, frequency counts, and the percentages based on the appropriate method. Percentages will be presented to 1 decimal place. Percentages will not be presented for zero counts.

Change from baseline will be calculated as the post-baseline value minus the baseline value. Percent change from baseline is defined as $(100 \times [\text{post-baseline} - \text{baseline}] / \text{baseline})$. Percent improvement from baseline is calculated as the positive percent change from baseline if a higher value at post-baseline means improvement from baseline. Similarly, percent improvement from baseline is calculated as the negative percent change from baseline if a lower value at post-baseline means improvement from baseline. If the baseline value is missing for a particular variable, then the change from baseline and the percent improvement from baseline will not be calculated.

Data collected at early termination visits will be mapped to the next planned visit number for that patient. For by-visit summaries, only visits in which a measure was scheduled to be collected will be summarized. Unplanned/unscheduled measurements will be excluded from the mixed-effects model of repeated measures (MMRM) analysis. However, the data will still be used in other analyses; such analyses include, but are not limited to, shift analyses and modified baseline observation carried forward (mBOCF) endpoint analyses.

All confidence intervals (CIs) and statistical tests will be 2-sided with an α level of 0.05 unless specified otherwise. P-values that are greater than or equal to 0.001, and less than or equal to 0.999, will be presented to 3 decimal places. All other p-values that are less than 0.001 will be presented as <0.001, while p-values greater than 0.999 will be presented as >0.999. Confidence intervals will be presented to 1 more decimal place than the raw data.

Age, sex, and race will be reported on all by-patient listings unless otherwise specified. Sex will be abbreviated as follows: female (F) and male (M). Race will be abbreviated as follows: American Indian or Alaska Native (AI), Asian (AS), Black or African American (BL), Native Hawaiian or other Pacific Islander (NH), White (WH), and Multiple (MU).

Table RHCF.6.1 gives the treatment groups to be displayed for each treatment period and analysis population. Analysis populations are defined in Section 6.1.3. Note: “IXE” and “ADA” will be included in treatment group names for ixekizumab and adalimumab, respectively, in the statistical reports where applicable.

Table RHCF.6.1. Treatment Groups for Each Treatment Period and Analysis Population

Treatment Period	Analysis Population	Treatment Groups	Abbreviation	Comparison
Open-Label Treatment Period (Period 2)	Intent-to-Treat Population; Safety Population	Ixekizumab 80 mg Q4W (or Q2W/Q4W) Adalimumab 40 mg Q2W	IXE ADA	IXE vs ADA
Post-Treatment Follow-up Period (Period 3) ^a	Follow-up Population	Ixekizumab 80 mg Q4W (or Q2W/Q4W) Adalimumab 40 mg Q2W	IXE ADA	Not applicable

Abbreviations = ADA = adalimumab; IXE = ixekizumab; Q2W = every 2 weeks; Q4W = every 4 weeks.

^a Treatment group refers to the dosage regimen that the patient received immediately prior to entering the Post-Treatment Follow-up Period.

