5.1.3. Post-Treatment Follow-Up Period (Period 3)

All patients receiving at least 1 dose of investigational product will enter the Post-Treatment Follow-Up Period (Period 3), occurring from last treatment visit (LTV) during Period 2 or ETV up to a minimum of 12 weeks after that visit.

The required study visits should occur 4 weeks (Visit 801) and 12 weeks (Visit 802) after the last regularly scheduled visit in Period 2 (or the date of the patient's ETV), except for patients with a concurrent infection that requires systemic anti-infective therapy (described below).

If, at Visit 802, a patient's neutrophil count is ≥ 1500 cells/ μ L or greater than or equal to the patient's baseline neutrophil count, the patient's participation in the study will be considered complete unless the investigator determines additional follow-up may be necessary. An additional study visit (Visit 803) 12 weeks after Visit 802 may be required.

If, at the last scheduled visit or ETV, a patient's neutrophil count is <1500 cells/ μ L ($<1.50 \times 10^3/\mu$ L or <1.50 GI/L) and less than the patient's baseline neutrophil count, the following measures should be taken:

- Patients with concurrent infection: If there is a concurrent infection that requires systemic anti-infective therapy, the patient should receive appropriate medical care and a repeat test for neutrophil count should be performed at least Q4W (or sooner as appropriate) until resolution of infection. Upon resolution of infection, the neutrophil count should be monitored using the required study visits in the Post-Treatment Follow-Up Period (Period 3) design at Visits 801 (4 weeks after resolution of infection), 802 (8 weeks after Visit 801), and 803 (if necessary; 12 weeks after Visit 802); additional visits may be required depending on the degree of neutropenia.
- Patients without concurrent infection: If there is no concurrent infection that requires systemic anti-infective therapy, the neutrophil count should be monitored using the required study visits in the Post-Treatment Follow-Up Period (Period 3) design, Visits 801 (4 weeks post ETV or last regularly scheduled visit), 802, and 803 (if necessary); additional visits may be required depending on the degree of neutropenia.
- For Visit 801 and subsequent visits, the following monitoring applies:
 - As long as a patient's neutrophil count is <1000 cells/μL (<1.00 × 10³/μL or

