10.3.1.2.1. Nonresponder Imputation

Missing data for categorical efficacy and health outcome measures will be imputed using the nonresponder imputation (NRI) method. Patients will be considered nonresponders if they do not meet the clinical response criteria or have missing clinical response data at the time point of analysis. Randomized patients without at least one post-baseline observation will also be defined as nonresponders for the NRI analysis.

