6.4. Handling of Dropouts or Missing Data

6.4.1. Non-Responder Imputation (NRI) for Clinical Response

Analysis of categorical efficacy and health outcome variables will be based on treatment success/failure. This approach yields results numerically identical to non-responder imputation (NRI), but it is interpreted differently. Patients will be considered treatment failures (or non-responders) if they do not meet the clinical response criteria or have missing clinical response data at a particular time point of analysis.

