- The number and percentage of patients in the Post-Treatment Follow-Up Population completing each follow-up visit or prematurely discontinuing from the Post-Treatment Follow-Up Period, by treatment group, visit, and primary reason for discontinuation.

Patient allocation by region, country, and center/site will be summarized with number of patients who entered the study, number of ITT patients for each treatment group, number of patients discontinued from study treatment, and number of patients discontinued from study.

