		
 PASI 75/90/100 	Defined as at least 75%, 90%, or 100% improvement in PASI total score from baseline	Single item, missing if PASI total score is missing
ACR50 and PASI 100	Patients who achieve ACR50 and PASI 100 simultaneously.	
 Simultaneous ACR50 and PASI 100 		Missing if either ACR score or PASI score is missing.
Percentage of Body Surface Area (BSA)	The investigator will evaluate the percentage involvement of psoriasis on each patient’s BSA on a continuous scale from 0% (no involvement) to 100% (full involvement), in which 1% corresponds to the size of the patient’s hand (including the palm, fingers, and thumb) (National Psoriasis Foundation [NPF] 2009).	
 BSA 	Collected as a single item on the eCRF. Range from 0% to 100%	Single item, missing if missing.
		
 Change from baseline in BSA 	Calculated as: observed BSA – baseline BSA	Missing is baseline or observed value is missing

Measure	Description	Variable	Derivation/Comment	Imputation Approach if with Missing Components

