Appendix 2. Algorithm for Determining ACR Responses

Details presented in this appendix will use “x” as a generic symbol, and the appropriate number (either 20, 50, or 70) is to be filled in when implementing in dataset programming code.

ACRx response is defined as $\geq x\%$ improvement from baseline in tender joint count (68 counts) and $\geq x\%$ improvement in swollen joint count (66 counts), and $\geq x\%$ improvement in at least three of the following five items:

- Patient’s global assessment of arthritis pain;
- Patient’s global assessment of disease activity;
- Physician’s global assessment of disease activity;
- HAQ-DI;
- CRP.

The following abbreviations will be used throughout this appendix to refer to the items needed in the algorithm definitions:

Parameter	Abbreviation for the Parameter
% improvement in tender joint count	TJC68
% improvement in swollen joint count	SJC66
% improvement in patient’s assessment pain	PATPAIN
% improvement in patient’s global assessment of disease activity	PATGA
% improvement in physician’s global assessment of disease activity	PHYGA
% improvement in HAQ-DI	HAQ
% improvement in CRP	CRP

For all seven parameters mentioned above, % improvement at a visit is calculated as:

$(\text{baseline value} - \text{value at visit}) * 100 / \text{baseline value}$.

To calculate the *observed* ACRx response at a visit:

- **Step1:** If the patient discontinued from the study prior to reaching the visit, then STOP – assign ACRx response as blank (ie, missing). Otherwise, calculate the % improvement at the visit for all seven parameters as described above.
- **Step2:**
 - If TJC68 AND SJC66 are BOTH $\geq x\%$, then proceed to step3.
 - If both are nonmissing but one or both is $< x\%$, then STOP – assign the patient as a non-responder for ACRx.
 - If either or both are missing, proceed as follows:
 - a. If both are missing, then STOP – assign ACRx response as blank (ie, missing).
 - b. If one of TJC68 or SJC66 is missing and the nonmissing value is $< x\%$, then STOP – assign the patient as a non-responder for ACRx.

- c. If one of TJC68 or SJC66 is missing and the nonmissing value is $\geq x\%$, then STOP – assign ACRx response as blank (ie, missing).
- **Step3:** Consider the following five variables: PTPAIN, PTDISACT, PHYSDISACT, HAQ, and CRP.
 - If three or more items are missing, then STOP – assign ACRx response as blank (ie, missing).
 - If three or more items are nonmissing, then proceed with the following order:

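### Early-termination data are mapped to the next visit without a day window, so PASI 100 seen up to about 8 weeks early can count as Week 24 response; for ACR50 and the composite the rule is unsettled

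*SAP*

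**What the plan says.** SAP 6.1: "Data collected at early termination visits will be mapped to the next planned visit number for that patient". Neither document adds an analysis window. The protocol's Schedule of Activities places Visit 7 at Day 112 ± 4 and Visit 8 at Day 168 ± 4, with nothing between them. It schedules PASI, the joint counts, the VAS scores, HAQ-DI and hs-CRP at the ETV.

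Nonresponse is assigned on two grounds only. SAP 6.4.1: "Patients will be considered treatment failures (or non-responders) if they do not meet the clinical response criteria or have missing clinical response data". Protocol 10.3.1.2.1 likewise covers patients who do not meet the criteria or who "have missing clinical response data at the time point of analysis".

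The endpoint rules differ:
- PASI 75/90/100 (SAP Table RHCF.6.3): "Single item, missing if PASI total score is missing".
- ACR20/50/70 (SAP Appendix 2, Step 1): "If the patient discontinued from the study prior to reaching the visit, then STOP", after which the response is left blank.
- Composite (SAP Table RHCF.6.3): "Missing if either ACR score or PASI score is missing".

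**The concern.** There are two separate defects.

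The first is timing. A patient who stops treatment shortly after Week 16 and is clear of psoriasis at the ETV counts as a Week 24 PASI 100 responder, although nothing was measured near Week 24.

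The second is that the rules are not the same across endpoints. ACR has a discontinuation stop and PASI has none. If the stop applies to a mapped ETV, the same patient at the same visit can be a PASI 100 responder and a nonresponder on ACR50 and the composite. If it does not apply, all three use the early value. These are the primary endpoint and the two major secondary endpoints, tested in sequence, so the rule should be fixed before the Week 24 lock.

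**Working it through.** **Does Step 1 apply to a mapped ETV?** Two things are undefined: whether stopping treatment is the same as discontinuing from the study, and whether a mapped ETV counts as reaching the visit.
- Suggesting that it does not apply: SAP 6.8 tabulates separately the "number of patients discontinued from study treatment, and number of patients discontinued from study". Protocol 5.1.3 keeps patients in follow-up after treatment; if neutrophil criteria are met at Visit 802, their "participation in the study will be considered complete unless the investigator determines additional follow-up may be necessary".
- Suggesting that it applies: Protocol 8.1.1 and 8.2 send both groups along the same path (stop, ETV, Period 3). Protocol 9.4.5.4 treats stopping product as leaving the study, though only in the hepatitis B section.

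PASI 100 is unaffected by this question. ACR50 and the composite depend on it.

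**The plan's own figures** (275 per arm; rates from SAP 5.2).
- Exact two-sided Fisher power: composite (31.3% vs 13.6%) 99.87%; PASI 100 (46.9% vs 23.7%) 99.99%. The plan states about 99% for both.
- ACR50 noninferiority (43.8% vs 44.1%, margin 12 points): SE = sqrt(0.438 × 0.562/275 + 0.441 × 0.559/275) = 4.23 points. Power = Φ((12 − 0.3)/4.23 − 1.96) = 78.9%. The plan states 78%.

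**Patients exposed.** Assumptions: 28% dropout by Week 52 (from the 72% completion in Protocol 5.2), the same in both arms, with an ETV for every dropout.
- Constant hazard: 0.72^(16/52) − 0.72^(24/52) = 0.9039 − 0.8593 = 4.45%; × 275 = 12.2 per arm.
- Even spread: 28% × 8/52 = 4.31%; × 275 = 11.8 per arm.
- About 11 of these fall before Day 164, and about 1 falls between Day 164 and Day 168.
- Assumed range of 1% to 6%: 2.75 to 16.5 per arm.

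**PASI 100, under either reading.** If these patients respond at planning rates, 12.2 × 0.469 = 5.7 ixekizumab and 12.2 × 0.237 = 2.9 adalimumab responders are credited. The difference moves by 0.0445 × (46.9 − 23.7) = 1.03 points (0.23 at 1%, 1.39 at 6%). At half the planning rates it moves by about 0.5.

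**If Step 1 applies.** ACR50 and the composite are nonresponse for these patients, so neither has any ETV-driven shift.

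**If Step 1 does not apply.**
- Composite: 0.0445 × (31.3 − 13.6) = 0.79 points (0.18 at 1%, 1.06 at 6%).
- ACR50: 0.0445 × (43.8 − 44.1) = −0.01 points. With both rates multiplied by 1.0445, noninferiority power is 78.5%, against 78.9%.
- Error at the noninferiority null (44.1% vs 32.1%), judged against the windowed endpoint: SE = sqrt(0.441 × 0.559/275 + 0.321 × 0.679/275) = 4.11 points. Shift = 0.0445 × (32.1 − 44.1) = −0.53. One-sided error = 1 − Φ(1.96 + 0.53/4.11) = 1.8%. It is 2.3% at 1% exposure, 1.6% at 6%, and 2.1% if dropouts respond at half these rates.
- Exposure on ixekizumab would have to be 44.1/32.1 = 1.37 times that on adalimumab (about 16.8 vs 12.2 per arm) just to return this error to 2.5%.

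**The case against.** The mapping is prespecified, applies to both arms, and looks deliberate. Protocol 10.3.1.1, writing about measures not collected at every visit, drops off-schedule early-discontinuation data from the MMRM but keeps them for other categorical analyses. Appendix 2 computes the observed response at a visit, and SAP 6.1 gives the ETV a visit number. Read together, the mapped ETV could simply be that visit's record, with Step 1 blanking later visits only. The hepatitis B text is not a general definition. The ± 4 days are scheduling tolerances that neither document uses for analysis. Patients lost to follow-up may have no ETV, and the documents do not say whether the planning rates already include mapped ETV data.

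Much of this stands. The reading in which Step 1 does not apply is reasonable, the exposure figure is an assumption that may be too high, and adopting the scheduling tolerance is a choice. None of it removes the missing window or the difference between the PASI and ACR rules.

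A reader might also infer that the mapping contradicts the SAP's treatment-failure interpretation. It does not. SAP 6.4.1 defines failure by unmet criteria or missing data and does not mention stopping treatment, and the ITT definition in SAP 6.1.3 analyses patients whatever their adherence.

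**Conclusion.** The point holds as a minor one. Confidence is high only for the absent window and for the PASI/ACR rule difference. The sizes are illustrative: they rest on an assumed dropout pattern, an ETV for every dropout, balanced arms, and response at or below planning rates. On that basis the PASI 100 difference moves by about 1.0 point under either reading. The effects on the composite and ACR50 hold only if Step 1 does not apply, whereas the split between endpoints needs it to apply, so the two consequences cannot be added together.

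Two stronger inferences are not supported. One is that all three endpoints depend on how Step 1 is read; PASI 100 does not. The other is that the mapping inflates type I error for ACR50 noninferiority. With balanced exposure the change is slightly conservative against the windowed endpoint, and against the SAP's own mapped endpoint the nominal error stays at 2.5%. The documents indicate no imbalance towards ixekizumab.

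**What to change.** State one rule in SAP 6.1 and 6.4.1 for ACR, PASI and the composite, replacing the discontinuation stop in Appendix 2 Step 1:
- ETV data supply a planned visit's responder status only if the ETV falls within that visit's window. For Week 24 this is Day 168 ± 4, with the SAP stating that it adopts the protocol's scheduling tolerance as the ETV analysis window.
- Outside the window the visit is missing and counts as nonresponse on all three endpoints.
- Inside the window the observed value is used, whatever the date of last dose.
- The mapped-ETV version is reported as a sensitivity analysis.

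The cost is SAP wording, one programming rule and one extra table before the Week 24 lock. Reported response rates may be slightly lower.
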